### **G-Secondary Outcomes:**

#### **h- Sample Size:**

30 diabetic patients from outpatient retina clinic in Cairo university hospital.

#### **i- Source of Funding:**

Private-funding

#### **16- Time Plan**

Start Date: December 2017 for 6 months.

### ***Statistical Analysis:***

Data were collected, revised, coded and entered to the Statistical Package for Social Science (IBM SPSS) version 23. The quantitative data were presented as mean, standard deviations and ranges when their distribution found parametric and median with inter-quartile range (IQR) when their distribution found non parametric. Qualitative variables were presented as number and percentages. The comparison between groups regarding qualitative data was done by using Chi-square test. The comparison between two paired groups with quantitative data and parametric distribution were done by using Paired t-test. While comparison between more than two paired groups with quantitative data and parametric distribution were done by using repeated measure ANOVA test. The comparison between two paired groups with quantitative data and non-parametric distribution were done by using Wilcoxon Rank test. While comparison between more than two paired groups with quantitative data and non-parametric distribution were done by using Friedman test. The confidence interval was set to 95% and the margin of error accepted was set to 5%. So, the p-value was considered significant as the following: P-value > 0.05: Non significant (NS), P-value < 0.05: Significant (S) and P-value < 0.01: Highly significant (HS).

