**B-Inclusion Criteria:**

Diabetics (type 1 or type 2) more than 10 years durations with bilateral DME

Age: 20-80 years

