**d- Methodology:**

All patients meeting inclusion criteria in outpatient retina clinic, will have a full ophthalmological assessment including:

Past and present History.

Full Slit lamp examination.

Fundus examination.

OCT Macula Bilaterally

One eye of the same patient (randomly selected) will undergo laser treatment with Yellow Micropulse Laser 577-nm and the other eye (randomly selected) with Diode Micropulse Laser 810-nm.

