**f- Primary Outcomes:**

To detect the effect of Yellow Micropulse Laser 577 vs Infrared Diode Micropulse Laser 810 and their effect On Diabetic Macular Edema

As regards:

Visual acuity

Macular thickness via OCT

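### The SAP's only test for qualitative data is an unpaired chi-square, which is not valid in general for eye-level categories compared between fellow eyes of 30 patients

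*SAP*

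**What the plan says.** The protocol describes a within-patient comparison. Eligible patients are "Diabetics (type 1 or type 2) more than 10 years durations with bilateral DME" (Inclusion Criteria). Under Methodology, "One eye of the same patient (randomly selected) will undergo laser treatment with Yellow Micropulse Laser 577-nm", and the fellow eye receives the 810-nm laser. The sample size is "30 diabetic patients from outpatient retina clinic in Cairo university hospital", which is 30 fellow-eye pairs or 60 eyes.

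The primary outcomes are macular thickness by OCT and "Visual acuity". No scale is given for the latter, and no responder or category definition. The secondary-outcomes heading has no content.

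The SAP (Statistical Analysis) has four rules for comparing quantitative data, and all four are for paired groups. For two groups and parametric data, for example: "The comparison between two paired groups with quantitative data and parametric distribution were done by using Paired t-test". The others are the Wilcoxon test, repeated-measures ANOVA and the Friedman test. For categorical data it says "Qualitative variables were presented as number and percentages", and then: "The comparison between groups regarding qualitative data was done by using Chi-square test". No paired or clustered categorical method appears in either document.

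**The concern.** The only groups that the protocol defines are the two lasers, and these are applied to eyes of the same patients. A chi-square between them assumes 60 independent eyes. Fellow eyes of one diabetic patient share systemic disease, so their outcomes may well be correlated. The SAP allows for this in its quantitative rules but not in its qualitative rule. The same problem arises if one eye's category is compared between two visits.

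Patient-level traits such as sex or diabetes type are identical in the two arms, so a between-laser chi-square has no meaning for them. The rule therefore either has no use in the laser comparison or is applied to paired eyes.

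At stake is the p-value of any eye-level categorical result. Positive correlation makes the test conservative and wastes the precision that the paired design provides. Negative correlation makes it anti-conservative.

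**Working it through.** **Inputs.** From the documents: 30 pairs (Sample Size) and a 5% level (SAP). Assumed, because the documents are silent: a two-sided test, Pearson chi-square without continuity correction, event rates, and within-pair correlation ρ (phi). The plan states no power or response rate, so there is no figure of its own to reproduce.

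**Large-sample formula.** With equal rate p in both arms and n pairs, the true variance of the difference in proportions is 2p(1−p)(1−ρ)/n. Chi-square uses 2p(1−p)/n. Its actual size is therefore 2[1 − Φ(1.96/√(1−ρ))]. For ρ = 0.3, 1.96/√0.7 = 2.343, which gives 1.9%. For ρ = −0.2, 1.96/√1.2 = 1.789, which gives 7.4%.

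**Exact size.** All paired 2×2 tables with n = 30 were enumerated with multinomial probabilities, at equal rates of 30%, 40% and 50%:

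| ρ | Formula | Chi-square, exact | Asymptotic McNemar, exact |
|---|---|---|---|
| −0.2 | 7.4% | 7.2-7.6% | 4.8-5.2% |
| 0 | 5.0% | 4.9-5.2% | 4.4-4.8% |
| 0.2 | 2.8% | 2.8-3.0% | 4.3% |
| 0.3 | 1.9% | 1.9-2.0% | 4.3% |
| 0.5 | 0.6% | 0.6% | 4.5-4.7% |

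**Exact power (%)**, same enumeration, as chi-square / mid-p McNemar / asymptotic McNemar:

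| Rates | ρ = 0 | ρ = 0.2 | ρ = 0.3 |
|---|---|---|---|
| 50 v 25 | 52 / 50 / 50 | 52 / 58 / 58 | 52 / 64 / 64 |
| 40 v 20 | 39 / 37 / 37 | 38 / 43 / 43 | 37 / 48 / 49 |
| 30 v 10 | 50 / 46 / 46 | 50 / 54 / 56 | 50 / 59 / 63 |
| 20 v 5 | 45.3 / 36.3 / 40.3 | 44.2 / 40.8 / 49.4 | 43.3 / 43.3 / 55.5 |

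Mid-p overtakes chi-square at ρ of about 0.06 (50 v 25), 0.08 (40 v 20), 0.11 (30 v 10) and 0.30 (20 v 5). The exact (non-mid-p) McNemar test is a poorer choice: for 50 v 25 it has 48% power at ρ = 0.2 and 54% at 0.3.

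**Example.** Take 15/30 responders with one laser and 8/30 with the other. The pooled rate is 23/60, and χ² = (7/30)² / [(23/60)(37/60)(2/30)] = 3.455, p = 0.063, however the eyes pair up.

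- If 4 patients respond in both eyes, the discordant counts are 11 and 4 and ρ = 0. McNemar is 49/15 = 3.27, p = 0.071; mid-p is 0.077.
- If 6 respond in both eyes, the counts are 9 and 2 and ρ = 0.30. McNemar is 49/11 = 4.45, p = 0.035; mid-p is 0.039.

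The two data sets fall on opposite sides of 0.05, and chi-square cannot tell them apart.

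**The case against.** The strongest reply is that no affected analysis exists on paper. No categorical endpoint, responder definition or visit schedule is given, and every rate and correlation above is assumed. This stands, and it is why the point is conditional and minor.

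A second reply is that the sentence refers only to groups. It may be meant for independent subgroups such as type 1 and type 2 patients, so that at most a paired test is missing. The SAP does not call the chi-square ordinary or Pearson; that is a reading, supported by the word paired appearing in every quantitative rule and not in this one. Both diabetes types are enrolled, but no subgroup comparison is planned. As written, the rule covers all qualitative comparisons between groups. The reply therefore does not remove the gap.

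A third reply is that positive correlation only makes the test conservative. That is correct: it creates no false claim. The anti-conservative case needs negative fellow-eye correlation, and nothing in the documents suggests that.

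Two stronger readings should be resisted. A reader might infer that every eye-level chi-square p-value would be wrong, but at zero correlation its size is 4.9-5.2% at these rates. A reader might also take the SAP's rule for more than two paired groups ("While comparison between more than two paired groups with quantitative data and parametric distribution were done by using repeated measure ANOVA test") as proof that categories will be compared over time. Four laser-by-time cells, or template wording, would fit that sentence as well.

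**Conclusion.** The point holds as a minor, conditional defect. The SAP's one categorical rule does not fit its fellow-eye design and is not valid in general for eye-level categories. Under the assumed rates of 30-50%, the nominal 5% test has a true size between 0.6% (ρ = 0.5) and 7.6% (ρ = −0.2). At ρ = 0.3 it gives up about 12 points of power for 50% v 25% (64 − 52). Near zero correlation it does no harm and is slightly more powerful than the paired tests.

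A reader might infer that the primary analyses are compromised. The documents do not support that: macular thickness and numeric visual acuity fall under the paired quantitative rules and are unaffected. Nor do the figures make one version of McNemar's test obligatory. The asymptotic version stays at or below about 5.2% in the cases run, and its power is at least that of mid-p.

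**What to change.** Replace the chi-square sentence in the SAP with:

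> Binary eye-level outcomes will be compared between lasers, or between two time points in the same eye, by McNemar's test (asymptotic or mid-p, chosen in advance), with the paired difference in proportions and its 95% CI. Outcomes with more than two categories will use a marginal-homogeneity test, and binary outcomes at more than two time points Cochran's Q. Chi-square will be used only for independent patient subgroups, if any.

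The authors should strike one of the two McNemar versions before the text is final. It would also help to state the visual acuity scale and whether any categories will be formed from it.

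The cost is one sentence and no extra data. The SAP is written in the past tense. If a categorical comparison of eyes has already been run, a binary result can be recomputed from its two discordant-pair counts.

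There is a statistical price if fellow eyes are uncorrelated. In the cases tabulated, asymptotic McNemar then has about 2 to 5 points less power than chi-square. Mid-p has about 2 to 4 points less, and 9 less at 20% v 5%. Mid-p is also very conservative for rare events. At a 10% rate its size is 2.8% against 5.4% for chi-square at ρ = 0, and 1.5% against 2.2% at ρ = 0.3. At a 5% rate it is 0.75% against 2.84%, and 0.25% against 0.95%. If rare categories are expected, that favours the asymptotic version.

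### The SAP leaves the baseline OCT unused and the compared quantity open; for roughly normal data a baseline-adjusted regression of between-eye thickness differences is the safer, usually more precise choice

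*SAP*

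**What the plan says.** The SAP is a single paragraph that assigns tests by type of data. For two paired sets of quantitative data there are two entries: "The comparison between two paired groups with quantitative data and parametric distribution were done by using Paired t-test" and "The comparison between two paired groups with quantitative data and non-parametric distribution were done by using Wilcoxon Rank test". Which one applies depends on how the distribution turns out, as in the descriptive rule "median with inter-quartile range (IQR) when their distribution found non parametric"; no criterion is given. Repeated-measures ANOVA and the Friedman test are listed for more than two paired sets, without naming factors or visits. No covariate or regression appears.

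The protocol (15d, Methodology) describes a within-patient design: "One eye of the same patient (randomly selected) will undergo laser treatment with Yellow Micropulse Laser 577-nm and the other eye (randomly selected") the 810-nm laser. The same section lists "OCT Macula Bilaterally" in the assessment of eligible patients, ahead of the sentence on laser. Visual acuity is not named in that list. Section 15f gives the outcome as "Macular thickness via OCT", with no assessment time and no mention of change. Section 15h gives "30 diabetic patients from outpatient retina clinic in Cairo university hospital", with no calculation. Section 16 gives only "Start Date: December 2017 for 6 months".

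**The concern.** Three things are open in the comparison that answers the trial's question. The SAP does not say that its two-sample paired test is the one between lasers; the same sentence would fit a before-versus-after test within one eye. It does not say whether final thickness or change is tested. And it makes no stated use of a baseline that the trial will have measured in both eyes.

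The precision of final value and of change depends on a correlation nobody has stated, so neither is a safe default with 30 pairs. A regression on the baseline difference largely removes the need to guess when data are roughly normal. Left open, the choice could also be made after the results are known.

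**Working it through.** **No figure to reproduce.** The documents give no effect size, SD, power or correlation behind the 30 patients. What can be compared is the precision of the candidate analyses with 30 pairs.

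**Inputs.** From the documents: n = 30 pairs (protocol 15h and 15d) and a 5% level (SAP; two-sided assumed, in line with its 95% interval). Assumed: roughly normal data; rho from 0 to 0.7; effects of 0.2 to 0.8 SD of the follow-up between-eye difference.

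**Definitions.** For each patient, D0 and D1 are the differences 577 nm minus 810 nm at baseline and follow-up. Rho is the correlation of D0 with D1, not the correlation within a single eye. Let s = SD(D0)/SD(D1). Random allocation of eyes gives D0 an expected value of zero.

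**Variance, in units of SD(D1)²/n.**
- Final value: 1.
- Change: 1 + s² − 2·rho·s, which is 2(1 − rho) when s = 1.
- Regression of D1 on D0, intercept at D0 = 0: (1 − rho²)(1 + 1/(n − 3)) = (1 − rho²)(28/27). This does not depend on s.

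With s = 1:

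| rho | Final | Change | Adjusted |
|---|---|---|---|
| 0 | 1.00 | 2.00 | 1.04 |
| 0.3 | 1.00 | 1.40 | 0.94 |
| 0.5 | 1.00 | 1.00 | 0.78 |
| 0.7 | 1.00 | 0.60 | 0.53 |

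**Break-even with final values.** (1 − rho²)(28/27) = 1 gives rho² = 1/28, so rho = 0.19, or about 0.20 allowing for the lost degree of freedom.

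**Largest cost.** The change variance can be written (1 − rho²) + (s − rho)², so it is never below 1 − rho²; nor is the final-value variance of 1. The adjusted variance therefore exceeds either by at most 28/27 − 1 = 3.7%, for any s.

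**Power.** Noncentral t, with noncentrality effect × √30 / √variance; 29 df for the simple tests and 28 for the regression. At rho 0.5 and s = 1, where final value and change are equally precise:

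| Effect (SD) | Final or change | Adjusted | Gain (points) |
|---|---|---|---|
| 0.2 | 18.4% | 22.4% | 4 |
| 0.3 | 35.5% | 43.6% | 8 |
| 0.5 | 75.4% | 85.0% | 10 |
| 0.8 | 98.8% | 99.8% | 1 |

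At 0.5 SD and s = 1, power for final, change and adjusted is 75.4/46.5/73.8% at rho 0, 75.4/60.9/77.7% at rho 0.3 and 75.4/92.7/95.3% at rho 0.7. Over rho 0–0.7 and s 0.75–1.25, the largest shortfall of the regression against the better simple test at this effect is 1.6 points.

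**Type I error.** In simulated normal data with no laser effect, the zero-centred intercept rejects about 5% of the time. Rejecting when either the final-value or the change paired t-test is significant gives about 8–10% over rho 0–0.7 and s 0.75–1.25.

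**The case against.** The strongest reply is that the paired tests are sound and adjustment is an optional refinement. Much of this stands. With lasers allocated to eyes at random, final value, change and regression all estimate the same effect. Below rho of about 0.2 the regression gains nothing over final values, and at rho 0.3 with an effect of 0.5 SD it gains only 2 points over them.

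Three stronger readings are tempting, and the documents support none of them.
- *That the analysis is biased or invalid.* It is not, for the reason just given.
- *That omitting the covariate costs up to 29 points of power.* At 0.5 SD, change is 29 points below final values at rho 0 (75.4 − 46.5), and final values are 17 below change at rho 0.7 (92.7 − 75.4). Those gaps are between the two simple tests. The covariate's own gain over the better of them is at most about 10 points at s = 1, and 0.5 SD is close to the most favourable effect size.
- *That 8–10% is the trial's error rate, or a ceiling on it.* It applies only if the better of two results were reported, and nothing shows that this was intended. Nor is it a bound: allowing either test on either quantity gives about 10–11%, and the visit is open too.

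It can also be said that repeated-measures ANOVA might bring in the baseline. It might, since two eyes at two times make four paired sets, but no factors are named, so this settles nothing.

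Normality matters. In simulated heavy-tailed data (t with 3 df, effect 0.5 SD), the regression falls 10–12 points below the better Wilcoxon version at rho 0, 7–8 at rho 0.3 and 2–4 at rho 0.5–0.7. Least squares should not displace Wilcoxon there, so a switch by distribution remains, as does the final-or-change choice on that branch. Finally, the SAP is in the past tense, so follow-up data may already have been seen.

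**Conclusion.** The point holds as a recommendation about efficiency and an unfixed analysis, limited to macular thickness and roughly normal data. Against either simple test the regression risks at most 3.7% in variance. In return it gives, with equal SDs, a 22% reduction against both at rho 0.5; at rho 0.7 the reduction is 47% against final values and 12% against change (0.53/0.60 = 0.88). The power gain at rho 0.5 runs from 1 to 10 points depending on the effect.

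These sizes rest on rho, the SD ratio and the effect size, none of which the documents give. The textual gaps do not depend on them: the SAP fixes no covariate, does not say which pair is compared, and does not choose between final value and change. If only before-versus-after tests within each eye were run, there would be no direct comparison of the lasers; the wording permits that reading but does not establish it.

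**What to change.** For macular thickness, name as the primary 577-versus-810 analysis a linear regression of each patient's follow-up between-eye difference (577 minus 810), at one named assessment time, on the baseline between-eye difference. Report the intercept with its 95% CI. Leave the baseline difference centred at zero, its expected value under random allocation; centring at the sample mean would return the unadjusted mean difference.

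Keep the paired t-test as a sensitivity analysis. Keep Wilcoxon for clearly non-normal data. Before follow-up data are seen, write down the criterion for that switch and whether the paired tests use final values or change. If the data have already been seen, say so and report the adjusted result alongside the others. Apply the same to visual acuity only if its pre-laser value is recorded.

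The cost is SAP wording, one degree of freedom and, for roughly normal data, at most 3.7% in variance (about 1.6 points of power at 0.5 SD). No extra patients or procedures are needed for thickness, and linear regression in SPSS gives the intercept and its interval.

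### Does the SAP's rule for three or more paired groups misfit a two-laser trial and leave the 577-nm versus 810-nm test undefined?

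*SAP*

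**What the plan says.** The protocol's Methodology section (15-d) sets the pairing: "One eye of the same patient (randomly selected) will undergo laser treatment with Yellow Micropulse Laser 577-nm and the other eye (randomly selected"), with the 810-nm laser. Section 15-f gives the question, "To detect the effect of Yellow Micropulse Laser 577 vs Infrared Diode Micropulse Laser 810 and their effect On Diabetic Macular Edema", and names two outcomes, visual acuity and macular thickness on OCT. Section 15-h gives 30 patients.

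The SAP's Statistical Analysis section is one general paragraph. For two paired groups it says: "The comparison between two paired groups with quantitative data and parametric distribution were done by using Paired t-test", with a Wilcoxon test when the data are not normal. For three or more it says: "While comparison between more than two paired groups with quantitative data and parametric distribution were done by using repeated measure ANOVA test", and then "While comparison between more than two paired groups with quantitative data and non-parametric distribution were done by using Friedman test". On error it says "The confidence interval was set to 95% and the margin of error accepted was set to 5" per cent. It does not say what the paired groups are, and it mentions neither laser, neither outcome and no visit.

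On timing, section 15-d introduces the assessments with "All patients meeting inclusion criteria in outpatient retina clinic, will have a full ophthalmological assessment including", followed by a list that comes before the laser allocation. No assessment after the laser is listed. Section 16 says only "Start Date: December 2017 for 6 months".

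**The concern.** Each patient receives only two lasers, so the groups in the rule for three or more cannot be lasers. They could be measurement times within one laser. A Friedman test or a one-factor ANOVA then describes change over time but contains no laser term. They could also be laser-by-time columns laid side by side, in which case an improvement shared by both eyes can produce a small p-value although the lasers are equal.

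The rule also implies at least two follow-ups, and the protocol lists none. The fellow-eye test could therefore be run at several visits, on change from baseline or on the value at the visit, and the SAP calls every p-value below 0.05 significant. At stake is whether the stated 5% applies to the answer to the objective, and whether a significant result could reflect something other than a laser difference.

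**Working it through.** **1. Which rule answers the objective.** Two lasers, one per eye, randomised within patient, make two paired groups. The SAP's rule for that case is the paired t-test or Wilcoxon test. With 30 complete pairs at two-sided 0.05 (sidedness assumed), the paired t-test has 80% power at a standardised paired difference of 0.529. The protocol gives no power, effect size or SD, so its 30 cannot be reproduced; this figure only shows that the test works at that size.

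**2. What the other rule can mean.**
- *Visits within one laser.* Friedman and repeated-measures ANOVA are valid here. Section 15-f asks about each laser's effect on the oedema as well as the comparison, so change within a laser is of interest in itself.
- *A laser-by-time repeated-measures ANOVA.* The SAP does not say its ANOVA has one factor. With two lasers and two times, the interaction F equals the square of the paired t on the between-eye difference in change, t² with 29 df. It therefore keeps 5% whatever improvement the eyes share. In simulation with identical lasers, both improving by 0.3 to 0.5 SD, the laser and interaction terms reject in about 5% of trials.
- *Four flat columns, with the overall p read as a laser effect.* This would mislead: 23% to 95% of trials reach p < 0.05 when identical lasers both improve by 0.3 to 0.5 SD. No sentence in either document calls for it.

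**3. What the open visit and form of outcome could cost.** Assumptions, none of them in the documents: one outcome, 30 pairs, normal data, identical lasers, and between-eye differences D with equal variance and correlation r between any two times.

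The correlation between the final value D₁ and the change D₁ − D₀ is (1 − r)/√(2(1 − r)) = √((1 − r)/2), that is 0.59, 0.50 and 0.39 at r = 0.3, 0.5 and 0.7. The two tests overlap only in part, so taking either one raises the error. Simulated chance of at least one p < 0.05:

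| Choice left open | r = 0.3 | r = 0.5 | r = 0.7 |
|---|---|---|---|
| None (one named test) | about 0.05 | about 0.05 | about 0.05 |
| One visit; change or value | 0.086 | 0.092 | 0.093 |
| Two visits; value only | 0.094 | 0.091 | 0.085 |
| Two visits; change only | 0.090 | 0.090 | 0.089 |
| Two visits; change or value | 0.159 | 0.163 | 0.160 |

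**4. Does one form answer a different question?** No. Eyes are randomised within patient, so the expected baseline difference is zero, and change and final value estimate the same laser effect. Only precision differs. The standardised effect on change is 0.529/√(2(1 − r)):
- r = 0.3: 0.447, power 66%
- r = 0.5: 0.529, power 80%
- r = 0.7: 0.683, power 95%

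The value at the visit gives 80% throughout. Change is the more precise form only when r exceeds 0.5, and the documents give no r.

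**The case for a change.** The best case for acting is that neither document ties a test, a visit or a form of outcome to the 577-nm versus 810-nm question, and that settling this would need only wording. That is correct on the text. With a true difference of 0.529 SD, change and final value disagree on significance in 20% to 27% of simulated trials, so the choice can alter the headline. The visual-acuity scale and the OCT region are open too.

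Three things limit this case. First, the figures of 9% and 16% require that any one success among the options be taken as the answer, and the SAP does not say that. Second, a remedy would have to name a visit and a form of outcome, and the documents give no ground for choosing: there is no visit list and no correlation. Advice to name one visit and one measure leaves the blank where it was. Third, the SAP is written in the past tense. If results had already been seen, a choice made now would be post hoc and would not restore 5%.

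Confining the two-group rule to the laser contrast would also remove the SAP's only rule for a before-and-after comparison within one laser. Confining repeated-measures ANOVA to visits within a laser would shut out the valid laser-by-visit analysis.

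What stands is that the plan is thin on this point. It does not stand that a stated rule is wrong.

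**Conclusion.** No change to the plan follows. The fellow-eye comparison has a valid test in the SAP, the tests for three or more groups are valid over visits, and the harmful use of them is written nowhere. The remaining gap is unwritten detail: what the paired groups are, which post-laser visits exist, and which visit and form of each outcome carry the comparison. An analyst would ordinarily compare the 577-nm eye with its fellow by paired t-test or Wilcoxon, and keep the over-time tests for describing each laser.

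The most the gap could cost is a false-positive rate per outcome of about 9% with one choice open or 16% with two, instead of 5%. That rests on 30 complete pairs, normal data, at most two follow-ups, correlations of 0.3 to 0.7, and picking the best result after the fact. Having two outcomes is a separate matter and is not counted. A reader of the results should check that the laser claim rests on the between-eye difference and that the visit and form of outcome are stated.

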## **11- Objectives:**

To detect the effect of Yellow Micropulse Laser 577-nm vs Infrared Diode Micropulse Laser 810-nm In the Treatment of Diabetic Macular Edema

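### Two unranked primary outcomes are each judged at p<0.05 with no success rule, multiplicity rule or primary visit; if either can carry the claim, false-positive error exceeds 5%.

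*SAP*

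**What the plan says.** Protocol section 11 (Objectives) gives one aim and no hypothesis: "To detect the effect of Yellow Micropulse Laser 577-nm vs Infrared Diode Micropulse Laser 810-nm In the Treatment of Diabetic Macular Edema". Section 15f (Primary Outcomes) repeats it as "To detect the effect of Yellow Micropulse Laser 577 vs Infrared Diode Micropulse Laser 810 and their effect On Diabetic Macular Edema" and then names two measures, visual acuity and "Macular thickness via OCT". They are not ranked, and no time point is attached to either. Section 15d (Methodology) describes a paired-eye design: one eye of each patient gets the 577-nm laser and the other the 810-nm laser. It sets out an initial assessment but no follow-up assessment. Section 15h gives 30 patients. Section 16 gives a start date and a six-month plan, but no visits.

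The SAP is one paragraph. It names no endpoint, primary comparison or visit. On error it says "The confidence interval was set to 95% and the margin of error accepted was set to 5" (per cent), without saying whether this is per test or across the study. It then labels results: "So, the p-value was considered significant as the following: P-value > 0.05: Non significant (NS), P-value < 0.05: Significant (S", with a further label for p below 0.01. Besides the paired t-test and the Wilcoxon test it plans "While comparison between more than two paired groups with quantitative data and parametric distribution were done by using repeated measure ANOVA test", and "While comparison between more than two paired groups with quantitative data and non-parametric distribution were done by using Friedman test". It is written in the past tense: "Data were collected, revised, coded and entered to the Statistical Package for Social Science (IBM SPSS) version 23".

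**The concern.** With two primary outcomes and one threshold applied to each, the meaning of a positive study depends on a rule that is not written. Suppose thickness gives p just under 0.05 and visual acuity does not. The documents do not let a reader decide whether the trial has shown a difference between the lasers. If either outcome is enough, there are two chances of a false claim, each at 5%.

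The visit adds to this. Only two lasers are compared, so tests for more than two paired sets suggest measurements at several times. If so, the visit used for the main comparison is also open. Should the outcome rule or the visit be settled after the results are seen, the error rate cannot be known.

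**Working it through.** **Inputs from the documents.** Two primary outcomes (protocol 15f); threshold 0.05 per test (SAP); 30 eye pairs (protocol 15d and 15h); paired t-test (SAP).

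**Assumed, because the documents give no value.** Two-sided tests; correlation r between the two test statistics; number of visits and the correlation between them; standardised paired difference dz (mean of the within-patient differences divided by their SD).

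**Step 1: the plan's own figure.** The SAP's 5% is correct for a single test. The question is what happens with two.

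**Step 2: either outcome suffices, one visit, no true difference.** With r = 0 the error is 1 − 0.95² = 0.0975. In general it is 1 − P(|Z1| < 1.96, |Z2| < 1.96) for a bivariate normal pair with correlation r.

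| Assumed r | Either suffices, 0.05 each | Both required | Holm (smaller p below 0.025) |
|---|---|---|---|
| 0 | 9.75% | 0.25% | 4.9% |
| 0.5 | 9.1% | 0.9% | 4.7% |
| 0.8 | 7.8% | 2.2% | 4.0% |
| 0.9 | 7.0% | 3.0% | 3.6% |
| 0.95 | 6.5% | 3.5% | 3.3% |

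The third column is 0.05 + 0.05 minus the second. Simulated paired t-tests with n = 30 agree: for either-suffices, 9.6% at r = 0 and 7.1% at r = 0.9. With one-sided tests at 0.05 the either-suffices figures are 9.75%, 8.8%, 7.5%, 6.8% and 6.3%.

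**Step 3: rules that hold 5%.**
- Both must succeed: a false overall claim requires rejecting a true null at 0.05, so error is at most 5% even if one outcome truly differs.
- Fixed order: if the first null is true, any false claim starts by rejecting it, at most 5%. If the first truly differs, only the second can be falsely claimed, again at most 5%.
- One sole primary outcome: one test at 5%.
- Holm: at most 5% in every case.

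**Step 4: the visit is also free.** Assume a between-visit correlation of 0.5 to 0.8, a between-outcome correlation of 0 to 0.5, and that any outcome at any visit can carry the claim. Simulated paired t-tests (n = 30) give about 14% to 17% for two visits and 18% to 24% for three. The independent-test values are 1 − 0.95⁴ = 18.5% and 1 − 0.95⁶ = 26.5%.

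**Step 5: would the omnibus tests solve it?** A 5% repeated-measures ANOVA or Friedman test per outcome could limit multiplicity over visits. Two such tests, if independent and if either suffices, still give 1 − 0.95² = 9.75%.

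**Step 6: power with 30 pairs.** Noncentral t with 29 degrees of freedom and noncentrality dz × √30; critical values 2.045 at 0.05 and 2.364 at 0.025.

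| Assumed dz | Power at 0.05 | Power at 0.025 | Holm, per outcome, both truly differ | Both significant at 0.05, both truly differ |
|---|---|---|---|---|
| 0.4 | 56% | 44% | 49–50% | 32–49% |
| 0.53 | 80% | 70% | 75–77% | 64–75% |
| 0.7 | 96% | 92% | 94–96% | 92–94% |

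The last two columns are simulated over r = 0 to 0.9. The last column is also the power for the second outcome in a fixed order, because it is claimed only when both tests reject at 0.05.

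**Step 7: if results have already been seen.** Assume three visits, visit correlation 0.6 to 0.9 and outcome correlation 0.3 to 0.8. Holm over the two outcomes at the most favourable visit leaves an error of 6.9% to 11.7%. Holm over all six tests (smallest p against 0.05/6 = 0.0083) gives 2.5% to 4.2%.

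**The case against.** A reader might infer that the SAP promises 5% error across the study and breaks the promise. The text does not support that. The 5% is not said to be study-wide, so this is an incomplete rule and not a contradiction.

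A reader might also infer that the trial's false-positive rate is 9.75%. That figure needs an either-suffices rule, which is not written, and zero correlation. Visual acuity and thickness in the same eyes may well be correlated, and at r = 0.8 to 0.95 the figure is 7.8% to 6.5%. If both outcomes must succeed, or they are tested in order, or one is the sole primary, there is no excess. If they are declared two separate questions, each answered on its own, 5% per outcome is a defensible choice.

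These points limit the size and the certainty of the excess. They do not remove the gap, because none of these rules appears in either document and the reader cannot tell which applies. Several time points are likewise an inference from the planned tests. The ANOVA and Friedman tests could restrain testing over visits within an outcome, but the SAP names neither as primary nor as a gate to later comparisons.

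**Conclusion.** The point holds as an incomplete decision rule that should be repaired. With two unranked primary outcomes, a 0.05 threshold for each and no success rule, the plan does not hold the false-positive chance at 5% if either outcome can carry the claim. At one visit, with two-sided tests, the size is 6.5% to 9.75% over assumed correlations of 0.95 down to 0. It rises to roughly 14% to 24% if the visit may also be chosen from two or three; those figures are illustrative, since the documents give neither the visits nor the correlations. The absence of a success rule, a multiplicity rule and a primary visit needs no assumption. It would go too far to say that the error is inflated whatever rule the sponsor had in mind, or that requiring both outcomes is the only remedy.

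**What to change.** Change protocol sections 15d and 15f and the SAP as follows.

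1. Name one follow-up visit that all patients can reach within the six-month plan. State that visual acuity and OCT are measured at baseline and at that visit. Section 15d needs the change because it schedules no follow-up and does not list visual acuity by name (its list may not be exhaustive).
2. Define the primary comparison as the within-patient difference, 577-nm minus 810-nm, in change from baseline at that visit.
3. Control error over the two outcomes by one stated rule. Either use a fixed order (first outcome at 0.05, second at 0.05 only if the first is significant), or use Holm (smaller p against 0.025 and, only if that succeeds, larger p against 0.05). A sole primary outcome, or a rule that both must succeed, would also hold 5%.
4. Label all other visits and tests, including the repeated-measures ANOVA and Friedman tests, secondary with no confirmatory claim.

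The SAP's past tense leaves open whether the data have already been examined. If they have, report both outcomes at every visit, apply Holm over every outcome-by-visit test, and label the analysis post hoc. Correcting for the two outcomes alone would not cover a visit picked afterwards.

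The cost is wording and, if not already planned, the measurements at the named visit; no extra patients are needed. Under Holm, an outcome tested at 0.025 loses 12, 10 and 4 percentage points of power at dz of 0.4, 0.53 and 0.7. A fixed order keeps full 0.05-level power on the first outcome, but the second is lost whenever the first fails.
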